There are several major limitations in the discussed prior studies that support the *scientific premise* for this proposal. The first major limitation is the use of BMI to estimate offspring adiposity during infancy and childhood. BMI in adults is related to clinical outcomes, however the predictive value and usefulness in infants, children, and adolescents is less clear⁹³. The use of BMI in infants, children, and adolescents is further complicated by the inter-individual variability among children for periods of rapid growth for which BMI cannot distinguish changes in FM or lean mass. In infants and children, there is a twofold range of variation in fatness for a given BMI value⁹⁴. However, in studies using sophisticated methods to directly assess offspring body composition and AT distribution, relationships between maternal DHA and offspring body composition are supported⁷².

Another limitation is that information or variability on maternal pre-pregnancy BMI and GWG are limited or lacking in the Muhlhausler⁸⁹ and Hauner⁸⁰ et al. studies. The Muhlhauser⁸⁹ study has a mean maternal pre-BMI of 26 kg/m² with a range that had few obese women (23.2-30.5 kg/m²) and GWG was not collected and not included in the analysis. The sample from the Hauner et al. study was even leaner (22.3±3.0 kg/m²) and GWG was ~15.5±5.0 kg with no report on percentage excessive GWG. The ADORE cohort from which we will recruit in Kansas City so far has a mean pre-pregnancy BMI of 28.5±7.1 kg/m² with a wide pre-pregnancy BMI range (17.4-50.1 kg/m²). GWG data are not yet available in the ADORE cohort, however, in [name] prior DHA study (KUDOS) in Kansas City, the mean GWG was 16.4±7.1 kg with GWG classification of 62% excessive. Our study will provide important data from a representative cohort to understand when controlling for excess maternal weight and excess GWG, what effect DHA has on offspring body composition.

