For the parent RCT, the goal is equal enrollment at the 3 centers with 400 subjects enrolled at each center (total n=1200) and the anticipated attrition is 11%. The goal enrollment at Kansas City is n=400 subjects. The expected enrollment pace is 8-10 subjects/month, with completed enrollment by late 2019 (~42 months) providing adequate time for assessment of the offspring to 24 months. [name] prior Phase III trial (KUDOS) at one site only (KUMC) enrolled 350 subjects in 42 months despite a relatively slow enrollment in the first 6 months of the study. The enrollment pace for the KUDOS trial at Kansas City was 8-12 subjects/month.

C1b) Placebo and DHA supplementation: A marine algae oil source of DHA (DSM, Columbia, MD) will be provided in capsules. Specific capsules to be used are equivalent to Spring Valley

Algal-900 DHA Dietary Supplement Softgels, 450/mg per capsule. The algal oil capsules in this study provides 800 mg DHA in 2 1-g capsules and the higher DHA group of subjects will be asked to consume 2 capsules per day. The placebo control group will receive 2 1-g capsules containing half soybean oil and half corn oil. The soybean and corn oil combination does not contain DHA. Two capsules provide 80 mg of α -linolenic acid, a precursor of DHA. On average, US adults consume ~1000 mg/d of α -linolenic acid but can make only about ~40 mg DHA/day. Both capsules will be prepared and provided with orange flavor to mask the taste if there is eructation. The placebo and masked DHA capsules will be provided in bottles of 100 capsules (a supply for 50 days). The capsules are donated by DSM. DSM also donated 200 mg DHA capsules to both groups for daily use. These are already available commercially as a prenatal supplement under several product names. The 200 mg capsules will be provided in bottles of 135 capsules (135-day supply) and will be marked with an expiration date. Other fatty acids found in the capsules do not contribute significantly to the amounts in the diets of US women. DHA is the only fatty acid expected to change in the RBC-phospholipids (PL) of the supplemented group. Capsule compliance was excellent in our KUDOS trial, on average 74% of capsules were consumed. The parent trial is under an IND from the FDA, and the IND requires ongoing assurance of capsule purity.

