Maternal DHA levels are related to lower change in infant FM: Infant body composition was measured using the Pea Pod (n=62) at birth and 3 months. No prenatal DHA supplementation was provided and maternal RBC DHA was measured at 36 weeks in pregnancy and categorized by the median as high (>50th percentile) or low (<50th percentile). We first explored the main effect of maternal DHA status on differences in the change in infant FM. Offspring born to mothers with a high DHA status had a lower change in FM when compared to offspring born to mothers with a low DHA status. With the known effect of excessive GWG on infant FM, next we explored the interaction of maternal DHA status and GWG category on the change in infant FM. Maternal GWG was categorized as appropriate or excessive based on the 2009 IOM guidelines. Using ANCOVA, we examined the main effects and interaction of maternal RBC DHA status and GWG category on the change in infant FM. Confounding variables included in the model were maternal pre-pregnancy BMI, GWG, 3rd trimester maternal measured DHA, father's BMI, maternal race, household income, gestational age at birth, infant gender, infant age at test, and baseline variable of interest (ie., infant FM). The interaction was significant (p=0.028). In post-hoc analysis, no difference was found by maternal DHA status in offspring exposed to appropriate GWG. However, in offspring exposed to excessive GWG, infants exposed to low maternal DHA status had a greater increase in offspring FM (Δ 1499.0 g) when compared to infants exposed to high maternal DHA status (Δ 1026.4 g; p=0.038). A similar effect was found for body mass, however, no difference for the change in FFM was found. Therefore, in the offspring exposed to excessive GWG and high DHA status, the lower change in body mass was due to a lower accrual in FM and not FFM. See Table 2 for a summary of these results. These data are preliminary but promising considering no maternal prenatal DHA supplementation was provided.

and DHA status.					
Infant		Weight gai	in status	D L	
variable	DHA status	Appropriate($n=25$)Excessive ($n=37$)		r value	
Change in	<50 th percentile	2943.1 ± 810.9	3589.1 ± 965.3	p-int=0.045; p=0.060 post-hoc	
body mass (g)	>50 th percentile	3146.7 ± 926.9	2961.7 ± 796.6	by DHA status	
Change in %fat	<50 th percentile	12.9 ± 6.2	15.5 ± 7.0	p-int=0.033; p=0.083 post-hoc	
	>50 th percentile	15.2 ± 7.2	11.1 ± 6.1	by DHA status	

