Recruitment/screening							
Data collection							
Data collection							
Data entry							
Data collection ends							
Data analysis and							
writing							
Manuscript prep &							
submission							

D6) **Study timeline**: Listed in **Table 6** is the timeline for the study.

D7): **Statistical analyses**: The primary purpose of this study is to determine if there are differences in the offspring FM at 24 months when exposed prenatally to high vs. low DHA supplementation and if maternal GWG status impacts this relationship (appropriate or excessive GWG).

D7a) **Aim 1 analysis:** Using a two-way analysis of variance (ANOVA) on the 24 months FM, we will test for a statistical interaction between GWG group and DHA dose. The specific interaction from this ANOVA will test the contrast to **investigate if the supplement of 1000 mg DHA/day compared to 200 mg DHA/day during pregnancy can reduce infant FM at 24 months and specifically if this reduction is greater in offspring exposed to excessive GWG versus appropriate GWG.** A two sided t-test statistic (alpha=0.05) is calculated from the appropriate contrast from the two-way ANOVA (GWG and DHA).

D7b) **Aim 2 analysis:** A three-way analysis of variance (ANOVA) on the 2 year central FM, we will test for a statistical interaction between both GWG and DHA dose and offspring gender and DHA dose.

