D7c) **Longitudinal analysis:** Additionally, we will perform a linear mixed model to explore differences between the high vs. low supplement groups for infant FM and distribution. The dependent variable will be infant FM or infant central FM and the independent variable will be DHA group (fixed effect) and time (4 visits: 2 wks, and 6, 12, and 24 months). The model will include the fixed effects of treatment, time and the treatment-time interaction, with the subject effect treated as random to account for the dependence among repeated observations. This analysis allows for unbalanced data (allows for missing data). We will use exploratory analyses to investigate, in a univariate fashion, covariates. GWG and infant gender will be included as well as other potential covariates including parity, maternal age, pre-pregnancy BMI, parity, education level, maternal diet, infant diet, infant age at test, gestational age at birth, and socioeconomic status. An auto-regressive covariance structure will account for unevenly spaced visits. For missing outcome data, the data vector will be used to impute the missing value. Infant gender will be explored both as a confounder and as an effect modifier to account for differences in growth rates. We will analyze the data without confounding variables and repeat the analysis with confounding variables.

D7d) **Power calculation:** We performed a power analysis based on pilot data reported in **Table 2**. We calculated a total of n=120 would be required to answer the primary aim. Of the total n=120, we anticipate n=54 will experience appropriate GWG (45%) and n=66 will experience excessive GWG (55%) with each approximately equally allocated to low and high DHA supplementation groups. For the given effect size (population mean differences of -168 vs 304 grams), the power is 0.815. This means that 81.5% of studies would be expected to yield a significant effect to detect an interaction, rejecting the null hypothesis that the two population means are equal. The test is two-sided. Allowing for 33% attrition, this increases the sample size to n=180. To answer the primary aim in a second group of Spanish speaking subjects, we will increase the sample size by n=180 for a total sample of n=360.

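### The 0.815 power in D7d is computed from a 3-month Pea Pod contrast in unsupplemented women, and the plan does not show that it applies to Aim 1 (24-month DXA fat mass, 1000 vs 200 mg DHA)

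*Combined protocol and SAP*

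**What the plan says.** Section D7d rests the sample size on one calculation: "We performed a power analysis based on pilot data reported in" Table 2. It continues: "We calculated a total of n=120 would be required to answer the primary aim". For an effect size given as "population mean differences of -168 vs 304 grams" it concludes that "the power is 0.815". Allowing for 33% attrition raises 120 to 180. A second 180 is added to answer the same aim in Spanish-speaking families, for a total of 360.

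Section D2 describes the pilot behind Table 2. There were 62 infants, measured by Pea Pod at birth and at 3 months. On exposure it says: "No prenatal DHA supplementation was provided and maternal RBC DHA was measured at 36 weeks in pregnancy". The mothers were then split at the median.

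Aim 1 is set out in D7a: "Using a two-way analysis of variance (ANOVA) on the 24 months FM, we will test for a statistical interaction between GWG group and DHA dose". Section D5 makes DXA the instrument at every visit, and D5i limits Pea Pod to 2 weeks and 6 months. On the DHA background of the two arms, C1b says: "DSM also donated 200 mg DHA capsules to both groups for daily use". Agreement to take that supplement is also an inclusion criterion in Table 1.

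**The concern.** The pilot and Aim 1 differ in three respects that bear on power:

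- **Exposure.** The pilot compared observed high and low DHA status without supplements. Aim 1 compares two randomised doses, and the lower arm is itself assigned DHA.
- **Outcome.** The pilot measured a change over 3 months. Aim 1 tests a level at 24 months.
- **Instrument.** The pilot used Pea Pod. Aim 1 uses DXA, and Pea Pod is not used at 24 months.

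Power for this interaction depends on the ratio of the contrast to the SD. D7d gives neither quantity for 24-month DXA FM, and it does not argue that the pilot's ratio should hold there.

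The chain 120/180/360 is built on this one figure. If it stands unqualified, a null GWG-by-dose interaction could be read as the result of a study with 81.5% power for Aim 1, which the plan has not shown.

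**Working it through.** **Inputs.** From D7d: n=120, with 54 appropriate and 66 excessive GWG, about equally divided by dose, so cells of 27, 27, 33 and 33. From D7a: two-sided alpha 0.05. From Table 2, change in FM (mean, SD) in g:

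- appropriate GWG: low DHA 1189.5 (549.9), high DHA 1330.4 (640.7)
- excessive GWG: low DHA 1499.0 (622.4), high DHA 1026.4 (539.3)

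**Step 1: contrast and SD from Table 2.**

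- Low minus high DHA, excessive GWG: 1499.0 − 1026.4 = 472.6 g.
- Low minus high DHA, appropriate GWG: 1189.5 − 1330.4 = −140.9 g.
- Interaction: 472.6 − (−140.9) = 613.5 g.
- Pooled SD: √[(26×549.9² + 26×640.7² + 32×622.4² + 32×539.3²)/116] = 589 g. An unweighted pool gives 590 g.
- Ratio: 613.5/590 ≈ 1.04.

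**Step 2: reproduce the stated power.** SE = SD × √(2/27 + 2/33) = 589 × 0.367 = 216 g. The noncentrality is 613.5/216 = 2.84. The noncentral t on 116 df gives power 0.804, and the normal approximation gives 0.810. An SD of about 580 g would give 0.815 exactly. So the Table 2 contrast and SDs account for the stated figure to within about a point.

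**Step 3: try the effect size D7d prints.** 304 − (−168) = 472 g. Then 472/216 = 2.18 and power is 0.58. Reaching 0.815 with 472 g needs an SD of about 447 g, below all four Table 2 SDs. Nor does the printed pair match the DHA differences in Step 1 (−140.9 and 472.6 g). The 304 equals appropriate minus excessive GWG within high DHA (1330.4 − 1026.4 = 304.0), for which the low-DHA counterpart is 1189.5 − 1499.0 = −309.5, not −168. The printed effect size and the printed power therefore do not belong together.

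**Step 4: power for Aim 1 over assumed values.** The documents give no 24-month SD, so every SD here is an assumption. The pooled n=240 is 360 × 0.67 = 241, rounded, with cells of 54, 54, 66 and 66. With the contrast held at 613.5 g:

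| Assumed SD (g) | Power, n=120 | Power, n=240 |
|---|---|---|
| 590 | 0.80 | 0.98 |
| 700 | 0.66 | 0.92 |
| 800 | 0.54 | 0.84 |
| 1000 | 0.38 | 0.65 |

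The contrast may also differ at 24 months:

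- Halved to 307 g at SD 590 g: 0.29 (n=120) and 0.51 (n=240).
- Raised by half to 613.5 × 1.5 = 920 g: 0.87 at SD 800 g and 0.70 at SD 1000 g (n=120).
- Growing in proportion to the SD: 0.80 at every SD from the Table 2 ratio, or 0.815 if the baseline SD is 580 g.

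**Step 5: detectable interaction.** Solving the same formula for 80% power gives about 1.04 SD at n=120 and 0.73 SD at n=240. At an assumed 800 g these are about 829 g and 584 g.

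**Step 6: GWG mix.** D7d plans on 55% excessive. After section A9, the protocol reports for the earlier Kansas City trial that "the mean GWG was 16.4±7.1 kg with GWG classification of 62% excessive". With 62% (22.8 and 37.2 per dose arm), power at n=120 moves from 0.815 to 0.796 at SD 580 g, or from 0.804 to 0.784 at SD 589 g. That is about 2 points.

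**The case against.** The strongest reply is that nothing is hidden. D7d names Table 2, the table's title gives the birth-to-3-month window, and D2 says that the women were unsupplemented. The Specific Aims say that RCT data with direct infant body composition are lacking, so extrapolating from a pilot was a visible planning choice. This stands, and it limits the severity. It does not supply the missing step from the pilot to Aim 1.

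A reader might infer that the study is underpowered, or that 0.815 is too high. The documents do not support that:

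- The hypothesis concerns FM accumulation over the first 2 years, so the contrast in grams could grow with the SD.
- The 200 mg given to both arms might narrow the separation in DHA status, but no achieved red-cell DHA for 1000 vs 200 mg is given to set against the pilot's 3.8% vs 6.4%. D2 calls the pilot promising precisely because no supplement was given. Assigned is also not consumed: C1b reports 74% of capsules taken in the earlier trial.
- If the language groups are pooled, Step 4 gives 0.92 and 0.84 at SD 700 and 800 g, both above 0.815.

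Two further inferences should not be drawn. Table 2 labels its entries as means and standard deviations and lists covariates for the model, so the documents do not show that the power calculation used a covariate-reduced SD. The pilot's own share with excessive GWG (37 of 62) is not identified as a Kansas City figure; only the 62% is.

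**Conclusion.** The point holds in this form: 0.815 is in effect the power to detect again the pilot's 3-month Pea Pod interaction, about 1.04 SD, and the documents do not establish it as the power of Aim 1. The true power and the direction of any error are unknown. The attribution to the Table 2 contrast rests on the reproduction in Step 2 (0.804 to 0.810), because the effect size D7d prints gives only about 0.58.

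The dependence on unstated inputs is large: 0.38 to 0.80 at n=120 for assumed SDs of 1000 down to 590 g with the contrast held, and higher if the contrast grows. The choice between n=120 and n=240 matters as much. D7d justifies the second 180 as a test in a second group, and D7a does not say whether the groups are pooled. The GWG mix is minor.

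This should be fixed. It affects what a null interaction can be taken to show. The endpoint, test, alpha and sample size are untouched.

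**What to change.** Revise D7d as follows:

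1. Reconcile the printed pair of differences with Table 2 and with the stated power. Then label 0.815 (or its corrected value) as the power for the pilot's 3-month Pea Pod contrast in an unsupplemented cohort.
2. For Aim 1, state the GWG-by-dose interaction in 24-month DXA FM detectable at 80% power, for n=120 per language group and for n=240 pooled.
3. Base it on the SD of the 24-month scans available so far, pooled without using dose assignment. First deliveries were in November 2016 and the document is dated March 2020, so such scans may exist, but their number is not reported. If there are too few, give a stated assumed range.
4. Show power with both SD and contrast varied in both directions, as in Step 4, and the 62% GWG mix as a minor sensitivity.

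Leave the sample size as it is. The cost is one rewritten paragraph and one blinded SD calculation. The drawback is that the plan gives up a single favourable power figure for a range.

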This study will recruit offspring of women who participated in prenatal DHA supplementation intervention. Offspring body composition and AT distribution will be assessed at 2 weeks and 6, 12, and 24 months using dual energy x-ray absorptiometry (DXA).

RISKS TO HUMAN SUBJECTS

Human Subjects Involvement, Characteristics, and Design

- Patient recruitment and informed consent. All recruitment, consent, and data forms for 1. the study proposal will be approved prior to any enrollment. Informed consent for continued testing is obtained by a trained research team member with NIH-approved Human Subjects' protection certification. Consent includes the standard elements: a study description, the potential risks, benefits and options for non-participation. All subjects are informed they are free to withdraw from the study without changes in their usual care. Consent is documented as a signed form and will be kept in a locked file at the study office. The study is conducted in accordance with ethical principles founded in the Declaration of Helsinki. The IRB review includes a review of all appropriate study documentation in order to safeguard the rights, safety and well-being of the subjects. The protocol, informed consent, written information given to the subjects, safety updates, annual progress reports, and any revisions to these documents are provided to the IRB by the principal investigators. The method of obtaining and documenting the informed consent and the contents of the consent will comply with GCP and all applicable regulatory requirement(s).
- 2. Describe the characteristics of the subject populations and identify criteria for inclusion and exclusion. Subjects will consist of infants born to women who participated in a DHA supplementation RCT. A description of the women participating in the parent RCT is as follows: women will be between 12 and 20 wk gestation without medical conditions that put their pregnancy at higher than normal risk.
- 3. *Identify the sources of research material to be obtained from subjects.* Data to be acquired will be body composition and anthropometric measures, and information regarding the pregnancy from questionnaires (pre-pregnancy BMI, GWG, parity, infant diet, infant feeding practices, etc). All participants will be assigned a non-identifiable subject number. Data collected will be kept in [name] locked research laboratory. Only study personnel and [name] have keys to access this area. Electronic data will be kept on a password protected computer in [name] laboratory on the shared drive. Only personnel approved by HSC and on the protocol will have access to the data.
- 4. *Describe all potential risks*. No appreciable risk of physical, psychological, social, legal or other harm is expected. Assessment of infant body composition and skinfolds is very low risk. The DXA does emit radiation. Four total body DXA scans will be completed over 24 months. The amount of radiation exposure for one DXA scan is equal to 0.001 mSV or the equivalent of exposure to 3 hours of natural background radiation. As a comparison, one chest x-ray is equal to 0.1 mSV or 10 days of exposure to natural background radiation. Over the course of 24 months, the total radiation exposure will be under a day of background radiation exposure. This is minimal especially considered it is spread over 24 months.
- 5. Describe the procedures for protecting against or minimizing any potential risks. N/A. No known risks.
- 6. Discuss why the risks are reasonable in relation to anticipated benefits.
- 7. N/A. No known risks.
- 8. *Plan for monitoring and reporting problems*. Research staff will immediately report any adverse events to the study PI for review.
- 9. *Plan for handling study withdrawal/discontinuation*. Participants may discontinue study participation at any time in the study.

Adequacy of Protection Against Risks

Describe plans for the recruitment of subjects and the consent procedures to be followed. Recruitment will be open to all pregnant women that participated in the parent study. The KUMC IRB will review and approve this study prior to implementation. Participant recruitment will be conducted by trained study staff under the supervision the PI. Consent forms and HIPPA disclosure information per IRBs will be given to all subjects and their signatures' witnessed. The consent forms will include a description of the study, nature of the data collection, the potential benefits and adverse reactions anticipated. The research team personnel will abide by all tenets of the University confidentiality policies, as well as the Privacy Protection for Research Subjects. All research staff will remain current in their NIH required Human Subjects protection and HIPAA certification.

Data monitors and auditors from the IRBs, and regulatory authorities will have access to the patient's original medical records for verification of data gathered on the case report forms and to audit the data collection process. Subjects will be made aware of persons who may see their protected health information in the informed consent document and may choose not to enroll in the study based on the information provided them in accord with 2003 HIPAA regulations. The patient's confidentiality will be maintained and will not be made publicly available to the extent permitted by the applicable laws and regulations.

The investigators will conduct the study in compliance with the protocol given approval by the KUMC IRB. Any changes to the protocol will require written approval from these committees prior to implementation, except when the modification is needed to eliminate an immediate hazard(s) to patients or if the change(s) involves only logistical or administrative aspects of the trial. Any departures from the protocol will be fully documented in the case report form and source documentation. IRB review occurs each year and newly dates consent forms are issued. The Research Assistant will keep the study binder that includes all communication with the IRB and CVs for all study personnel, and study personnel approved roles. The ultimate responsibility for ensuring that the study binders are in order will fall to the PI ([name]).

Patient recruitment and informed consent. All recruitment, consent and data forms for the study proposal will be submitted to the KUMC IRB prior to enrollment using templates and educational materials formatted as previously IRB-approved in the pilot study. Informed consent will be obtained by trained research personnel who have completed the NIH-approved Human Subjects' protection certification. Consent includes the standard elements: a study description, the potential risks, benefits and options for non-participation. All participants will be informed that they are free to withdraw from the study without changes in their usual care. Consent will be documented as a signed form and will be kept in a locked file at the study office. The study will be conducted in accordance with ethical principles founded in the Declaration of Helsinki. The IRB will review all appropriate study documentation in order to safeguard the rights, safety and well-being of the subjects. The protocol, informed consent, written information given to the subjects, safety updates, annual progress reports, and any revisions to these documents will be provided to the IRBs by the investigator. The method of obtaining and documenting the informed consent and the contents of the consent will comply with GCP and all applicable regulatory requirement(s).

Only those women who consented to be contacted regarding additional studies in [name] RCT will be approached. At consent, women will be asked if they give permission for future contact and if yes, a database with willing names to be contacted will be created. These women will be approached regarding enrollment into this study. For each visit completed, subjects will

be paid \$125. Therefore, if subjects complete all study visits, they will receive \$500. The incentives to be given are reasonable for the amount of participant contact that the study entails.

Protection against risk. Although no appreciable risk of physical or mental harm is expected to result from the protocol, procedures for dealing with adverse effects are established. Subjects will be instructed to report immediately to the study coordinator if any health problem occurs and to call the PI ([name]) at any time if they have questions are concerns. In such an event, it is the PI responsibility to answer those concerns honestly and to reiterate to the subject that they should continue in the trial only if they feel entirely comfortable with it. Subjects who choose to withdraw from the study will be reassured if they indicate the desire to withdraw.

Subjects will be protected against the risk of breaking confidentiality by decoupling of names from databases. Each participant will be assigned a numerical study ID and informed consent forms that include the subject's signature will be stored separately in locked file cabinets. For ensuring confidentiality, these are generally acknowledged to be the best methods known for ensuring that names are not associated with data. Only selected research staff will have access to the subjects' data. Subjects' informed consent includes the HIPAA compliance documentation approved by the KUMC IRB. Research team personnel will abide by all tenets of the University confidentiality policies as well as the Privacy Protection for Research Subjects.

Potential Benefits of Proposed Research

Describe all potential benefits. There are no direct benefits for participation in the study outside of contributing to the knowledge base on this topic.

Data Safety and Monitoring Plan

Data security: All participants will be assigned a non-identifiable subject number. Data collected will be kept in [name] locked research laboratory. Only study personnel and [name] have keys to access this area. Electronic data will be kept on a password protected computer in [name] laboratory on the shared drive. Only personnel approved by HSC and on the protocol will have access to the data.

Data and safety monitoring plan for the current Observational follow up study: We are not providing any interventions but only monitor outcomes of the offspring born to women participating in the parent RCT. Monitoring will be handled by the PI and the research team. For this ancillary study, research staff will immediately report any adverse events to the study PI for review. The study PI will report to the study team and a decision will be made regarding any action that should be taken.

Safety Monitoring of the already approved and NIH funded Parent RCT trial

The parent RCT has already been vetted, approved, and deemed safe through rigorous peer review. Details for safety monitoring of the parent RCT are included below.

Adverse Events Analyses: Fisher's exact test will be used to compare the incidence of maternal and infant adverse events between treatment groups. All *p* values will be evaluated at the $\alpha = 0.05$ level. No adjustment for multiple comparisons will be made.

Definitions of an Adverse Event: An adverse event (AE) is any reaction, side effect or other undesirable event that occurs in conjunction with the use of the test product, whether or not the event is considered related to the test product. New and worsening signs and symptoms of underlying or emerging disease will be recorded as an adverse event. Any patient complaint reported will be recorded as an adverse event. Signs and symptoms considered normal for pregnant or delivering patients will be collected as adverse events to ensure that even problems common to pregnant women such as headache, (lower) back pain, (lower) backache, abdominal pain, abdominal cramps and nausea are not influenced by consuming the DHA capsules.

Definition of a Serious Adverse Event: Any adverse event occurring that results in the following is considered a serious adverse event (SAE): 1) death; 2) a life-threatening event; 3) inpatient hospitalization or prolonging of an existing hospitalization; 4) a persistent or significant disability/incapacity or 5) a congenital anomaly/birth defect. Medical events that may not result in death, be life-threatening, or require hospitalization may be considered an SAE when, based upon appropriate medical judgment, they may jeopardize the patient and may require medical or surgical intervention to prevent one of the outcomes listed above.

Safety Monitoring: A Data Safety Monitoring Board (DSMB) will monitor the study for safety. [name] (Professor in Biostatistics and Epidemiology Center at CCHMC), [name] (Neonatologist and The Medical Director of Clinical research for the Neonatal Netwrok) and [name] PhD (Pharmacology expert) will be the members of the DSMB in addition to [name], as the medical monitor. All adverse events that are not expected during pregnancy will be tracked from medical records and by periodic phone interview when the study coordinator calls to check for supplement compliance and tolerance. All adverse events will be documented in eResearch and in the study binder. SAEs will be reported to the Central IRB and the medical monitor ([name]) within 2 days of our becoming aware of them. The DSMB will provide and independent review of the ongoing data, patient reports, adverse events at least yearly, making their deliberation about safety using data of adverse events from all 3 recruitment sites. Through its reviews of the study, the DSMB will determine whether cumulative data indicates the need to change the research design, to modify information presented to participants, or to terminate the project. Any action taken to suspend or terminate the project will be reported to the Central IRB, NIH Office of Sponsored Projects and the program director at NIH. The DSMB and medical monitor will evaluate the final study manuscript(s) and final reports to assure results are fairly presented and conclusions are appropriate.

INCLUSION OF WOMEN AND MINORITIES

Inclusion of Women: We are targeting pregnant women who have participated in a RCT designed study to test the impact of high versus low prenatal DHA supplementation on moving early pre-term birth to late pre-term birth. This study will continue to follow this cohort by studying the impact of high versus low prenatal DHA supplementation on offspring body composition and AT distribution.

Inclusion of Minorities: We are including all racial/ethnic groups in this study. There will be no exclusion criteria based on race or ethnicity.

INCLUSION OF CHILDREN

We are targeting pregnant women who have participated in a RCT designed study to test the impact of high versus low prenatal DHA supplementation. We will follow the offspring born to these women from birth to 2 years old.

Data Access, Dissemination, and Authorship

The data generated by this project will be entered into a system developed and managed by [name] team in Biostatistics at KUMC. KUMC maintains an elaborate and secure digital networks for storage and remote access of data through encrypted and password-protected servers. Typically, with longitudinal projects like this one, decisions as to how and when to publish empirical reports is a difficult one. To resolve this issue, the research team will map out a preliminary dissemination plan that is principled yet flexible enough to allow for the clearest manner of presenting the results, and to determine the extent of authorship. This has been a satisfactory mechanism for the research team to address the issue of publication without conflict in their ongoing collaborations.
